5.0 TREATMENT PLAN

5.1 Neoadjuvant Treatment

Treatment will be administered on an outpatient basis. Patients will be instructed to make use of medication diaries (Appendices D and E) to act as a records for administration of PD 0332991 and anastrozole. Appropriate dose modifications are described in Section 6.0. No investigational or commercial agents or therapies other than those described below may be administered with the intent to treat the patient's malignancy.

Cycle 0 (Only applicable for PIK3CA Mutant and WT cohorts)

Before Cycle 1 Day 1 starts, patients who enrolled in the PIK3CA mutant or WT cohort should have completed Cycle 0. Cycle 0 therapy is 28 days of anastrozole (1mg PO daily) and, if premenopausal, goserelin 3.6mg SC every 28 days.

Cycles 1-5

Treatment with PD 0332991 combined with anastrozole (and goserelin if premenopausal) is to be 4 28-day cycles followed by a fifth cycle of 10-12 days duration consisting of daily PD 0332991 and anastrozole, with the last dose of both drugs to be given the day before surgery.

REGIMENT DESCRIPTION				
Agent	Dose	Route	Schedule	Cycle Length
PD 0332991	125 mg	PO	Daily (Days 1-21)	Cycles 1-4: 28 days
Anastrozole	1 mg	PO	Daily (Days 1-28)	Cycle 5: 10-12 days
Goserelin*	3.6 mg	SC	Q28 days	Adjuvant treatment: 28 days

* only if premenopausal; although it is preferred to be given on Day 1 of each cycle, it may be administered any day of the cycle to accommodate the Q28-day cycle for goserelin.

PD 0332991 should be taken with food. Anastrozole should be taken daily with or without food.

For both PD 0332991 and anastrozole:

- If a patient misses a day's dose entirely, she must be instructed not to make it up the next day but just take her regular dose the following day.
- If a patient vomits anytime after taking a dose, she must be instructed not to make it up but to resume subsequent doses the next day as prescribed.
- If a patient inadvertently takes an extra dose during a day, she must be instructed to not take the next day's dose.

Special Considerations for Cycle 5

Cycle 5 Day 1 of PD 0332991 may be delayed by up to 3 weeks to allow ANC to recover to $\geq 1500/\text{mcL}$ and platelets to recover to $\geq 100,000/\text{mcL}$ and other treatment related AEs

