If there is physical evidence for clinical progression with bi-dimensional tape, ruler, or caliper tumor measurements of the primary tumor, a mammogram and/or ultrasound of the breast should be done to confirm/rule out progressive disease. If there is physical evidence for clinical progression with clinical assessment of the lymph node mass, an ultrasound of the axilla should be done to confirm/rule out progressive disease.

If progression is confirmed by ultrasound **OR** mammographic imaging, discontinue the study drug and operate as soon as possible or begin other anti-neoplastic approaches such as chemotherapy or radiation therapy at the treating physician's discretion. NOTE: Other anti-neoplastic approaches such as chemotherapy or radiation must not be administered while the patient is taking study drug.

For these patients:

- Obtain the serum and plasma samples (can be obtained at surgery)
- Obtain core biopsies (two frozen in OCT and two formalin-fixed) before the patient receives non-protocol chemotherapy (could be obtained at surgery)
- Complete case report form indicating whether the patient will go to immediate surgery or begin other anti-neoplastic approaches such as chemotherapy or radiation therapy. If patient goes to immediate surgery, complete surgery and pathology case report forms.
- Follow-up for 30 days following the last dose of PD 0332991 or the resolution of AEs at least possibly related to PD 0332991, then yearly to complete 5 years of followup after surgery or until recurrence (whichever comes first).

If disease progression is not confirmed by ultrasound or mammographic imaging, study drug may be continued at the investigator's discretion, and the protocol followed as described. These patients are not eligible for adjuvant PD 0332991 therapy.

Clinical progression outside the primary site (i.e., the development of a new breast mass or the development of clinical suspicion for advanced disease) should lead to further imaging evaluation and if confirmed, study drug will be discontinued. Optional tumor biopsy and blood will be obtained prior to the subsequent neoadjuvant therapy or at the time of surgery if surgery is the next step. Subsequent management is at the investigator's discretion. The patient will go off study.

Patients in whom surgery is not performed will be observed for 30-60 days after last dose of study drug and will not undergo annual follow-up.

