10.2 Neoadjuvant Study Treatment Calendar (ALL Cohorts)

	≤ 14 days prior to registration	C1D1 ^A	C1D15 ±1 day	C2-5 D1±3 days	3 (+/-1) days prior to surgery	Off Study - Progression	Surgery ^B	Post-surgery ^C
TREATMENT								
Anastrozole ^E		Daily until the day of surgery (if no progression)						
Goserelin ^E		Every 28 days (if no progression)						
PD 0332991 ^F		3 weeks on and 1 week off ^{G,T}			D/C			
CLINICAL ASSESSMENT								
H&P, PS	X	X		X		X		X
Clinical meas. of breast lesions ^J	X	X		X		X		Exam
Adverse event assessment	X	X		X		X		X
CBC + differential	X			X	X ^Y			X
Serum chemistry ^K	X			X				X
Serum pregnancy test ^L		X			X	X		
Drug compliance assessment				X				
EKG (lead II) ^N	X						X	
RADIOLOGY								
Mammogram and US of breast and axillary masses ^O	X ^H			X ^H		X		
SAMPLE COLLECTION								
Tumor biopsies ^R		X ^W	X ^P	X ^Q		X ^S	X	
Research blood ^R		X ^U	X ^{P,V}			X ^S	X	

- A. C1D1 office visit, labs, EKG, as well as pre-PD 0332991 tumor biopsies may be done within 14 days prior to C1D1.
- B. Please refer to section 5.1. Surgery occurs between Cycle 5 day 11 and day 13 in patients who received Cycle 5 treatment. In patients who did not receive Cycle 5 treatment, surgery occurs 3 to 5 weeks following the last dose of PD 0332991.
- C. 30-60 days post-surgery, then yearly to document recurrence and survival for 5 years.
- E. Anastrozole (and goserelin if premenopausal) should have been started at least 28 days prior to C1D1 **(only applies to PIK3CA Mutant and Wild Type cohorts).
- F. Patients will keep a pill diary (Appendix D).
- G. If C1D15 Ki67 is > 10%, patient will discontinue PD 0332991 and be observed for AEs 30-60 days following the last dose, then followed per protocol. Further treatment is at the discretion of the treating physician.
- H. Prior to start of PD 0332991 (within 12 weeks prior to registration) and at the end of cycle 4 before surgery.
- J. 2D measurements of the breast lesion should be performed. Using a standard cm calibrated caliper, tape or ruler, the longest axis and the perpendicular axis of the tumor are to be measured and recorded in metric notation. In patients with synchronous lesions, it is recommended that both lesions be measured and biopsied the same if they are both >1cm with at least one dimension; otherwise, the dominant mass is followed clinically and by Ki67

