12.0 MEASUREMENT OF EFFECT

12.1 Neoadjuvant Treatment

Complete cell cycle arrest: This is defined as $\text{Ki67} \leq 2.7\%$, which will be assessed at C1D1, C1D15, and surgery. In patients without C1D15 Ki67, Ki67 on D15 of subsequent cycles could be used instead.

Clinical Evaluation: Prior to Cycle 0 (or performed during pre-registration for study NCI 9170), and at the end of each neoadjuvant treatment cycle cycles (that is, at the end of Cycles 1-4) the longest axis and the perpendicular axis of the measurable lesion should be measured and recorded in metric notation by tape, ruler or caliper technique on the case report forms.

Radiologic evaluation of tumor size: Mammogram and ultrasound imaging will be performed prior to Cycle 0 (or performed during pre-registration for study NCI 9170) and at the end of Cycle 4 combination therapy for bidimensional measurement of the tumor.

WHO criteria will be used to assess clinical and radiologic responses.

Complete Response (CR) is defined as the disappearance of all known disease based on a comparison between the pre-treatment measurements and the measurements taken at the completion of neo-adjuvant therapy (that is, at the end of cycle 4 neo-adjuvant combination therapy). In addition there is no appearance of new lesions.

Partial Response (PR) is defined as a 50% or greater decrease in the product of the bi-dimensional measurements of the lesion (total tumor size) between the pre-treatment measurements and the measurements taken at the completion of neo-adjuvant therapy (that is, at the end of cycle 4 neo-adjuvant combination therapy). In addition there can be no appearance of new lesions or progression of any lesion.

No Change (NC): a 50% decrease in total tumor size cannot be established nor has a 25% increase in the size of the lesion been demonstrated.

Progressive Disease (PD): A 25% or greater increase in the total tumor size of the lesion from its pretreatment measurements or the appearance of new lesions.

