12.2 Treatment Resistance

A patient is said to have resistance disease if her Ki67 is $> 10\%$ on biopsy taken on Cycle 1 Day 15 or if progressive disease is documented any time during neoadjuvant endocrine therapy.

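### Section 5.7 bars adjuvant PD 0332991 after unconfirmed progression, but no adjuvant entry rule in the available text excludes imaging-confirmed primary or nodal progression on the drug

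*Combined protocol and SAP*

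**What the plan says.** Section 5.7 separates three situations.

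- **Growth of the primary tumour or lymph node mass, confirmed by ultrasound or mammogram.** The instruction is to "discontinue the study drug and operate as soon as possible or begin other anti-neoplastic approaches". Samples are collected and the patient is followed yearly to 5 years after surgery or until recurrence. Adjuvant drug is not mentioned.
- **Growth suspected but not confirmed.** "If disease progression is not confirmed by ultrasound or mammographic imaging, study drug may be continued" at the investigator's discretion. The paragraph ends: "These patients are not eligible for adjuvant PD 0332991 therapy".
- **Confirmed progression outside the primary site**, which includes a new breast mass or suspected advanced disease. Drug stops and the patient goes off study.

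Adjuvant entry is set in Section 3.5, which Section 3.0 makes the screening standard. Sections 3.5.1 and 5.3 define benefit by Ki67. The patient must either be one of 26 named-by-result patients from the first cohorts (above 2.7% at C1D1, at or below 2.7% at C1D15) or be in the endocrine resistant cohort with C1D15 Ki67 of 10% or less. Appendix C is the matching worksheet.

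Section 12.1 defines progressive disease as "A 25% or greater increase in the total tumor size of the lesion from its pretreatment measurements" or new lesions. Section 12.2 counts a patient as resistant "if progressive disease is documented any time during neoadjuvant endocrine therapy".

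**The concern.** The only explicit progression bar is attached to the milder finding. Read as written, the adjuvant option is open after confirmed growth on the drug and closed after growth that imaging did not confirm. The criteria and worksheet used at registration carry neither exclusion.

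What is at stake is exposure to up to 23 further cycles of a drug on which the tumour has already grown. The exposure has a cost: Section 1.7 reports that, with letrozole in metastatic disease, neutropenia was grade 3 in 55% and grade 4 in 6% of the combination arm (55 + 6 = 61%).

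**Working it through.** The plan gives no figure to reproduce, so the check sets the passages side by side.

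| Place | Confirmed growth, primary or nodal | Growth not confirmed |
|---|---|---|
| 5.7 | Drug stopped, surgery or other therapy, yearly follow-up; silent on adjuvant drug | Drug may continue; adjuvant drug barred |
| 3.5.1 (8 items) | No item | No item |
| 3.5.2 (10 items) | No item; metastatic disease is the only disease-status exclusion | No item |
| 5.3 | Benefit judged by Ki67, no progression condition | Same |
| Appendix C (8 inclusion, 10 filled exclusion items) | No item | No item |
| 10.3 | Refers to 3.4, which has no progression item | Same |

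**1. Whom the bar covers.** The sentence closes the paragraph on unconfirmed progression, so its grammatical subject is that group. No other passage gives it a different one.

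**2. Item count.** Section 3.5: 8 + 10 = 18. Appendix C: 8 + 10 = 18 (exclusion numbers 1-9 and 11; numbers 10 and 12 have no text in the available copy). Items naming primary or nodal progression during neoadjuvant therapy: 0 of 18 in each.

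**3. Can confirmed growth follow a passed benefit test?** Section 5.1 says treatment "is to be 4 28-day cycles followed by a fifth cycle of 10-12 days duration". Cycles 1-4 last 4 × 28 = 112 days. The biopsy is on day 15, or as late as day 20 under the notes to 10.2. That leaves 112 − 15 = 97 days, or 112 − 20 = 92 days. Section 12.1 plans tumour measurements at the end of each of the 4 cycles. So the sequence is possible. The day count shows opportunity, not frequency.

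**4. Two women traced through the rules.**
- Woman A is in the endocrine resistant cohort with C1D15 Ki67 of 10% or less. Her primary tumour later grows and ultrasound confirms it. She stops drug, has curative-intent surgery and has no metastases. She meets the Ki67 test and the surgery item in 3.5.1, and the metastatic exclusion does not apply. Every written disease-related criterion is met.
- Woman B has the same Ki67. Growth is suspected on calipers and imaging does not confirm it. She completes treatment and surgery. She also meets every disease-related item in 3.5 and Appendix C, but 5.7 bars her.

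**5. The reference in 10.3.** It makes adjuvant entry conditional on Section 3.4. But 3.4.2 excludes prior surgery for this cancer and any prior Cdk4 inhibitor, while adjuvant candidates must have had both surgery and neoadjuvant PD 0332991. No candidate can satisfy 3.4. Section 10.3 also uses Ki67 below 10%, where 1.8, 3.5.1, 5.3 and Appendix C use 10% or less; this matters only at exactly 10%.

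**6. Ceiling on candidates.** 26 + 37 = 63 if the endocrine resistant cohort completes both stages, or 26 + 12 = 38 if it stops at Stage 1. The groups do not overlap, because 3.4.2 excludes a prior Cdk4 inhibitor. Either total would need every endocrine resistant patient to have Ki67 of 10% or less and to undergo surgery.

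**The case against.** The best defence is that the intent is clear. Section 12.2 calls progressors resistant. Section 5.6 makes confirmed progression a stopping rule in both the neoadjuvant and the adjuvant phase. The 10.2 calendar has a column headed "Off Study - Progression". The yearly post-surgery follow-up that 5.7 gives confirmed progressors matches the schedule that the schema footnote and 10.3 give to patients without adjuvant drug. On this view one sentence is merely out of place, and central confirmation of eligibility with source documents (4.2, 4.2.1) would catch a bad case.

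This is good evidence of intent, but none of it is an adjuvant entry rule. Section 5.6 ends treatment in each phase; it does not stop a restart between phases. Section 5.7 says off study only for progression outside the primary site. Central review lowers the risk, but the reviewer checks against criteria that contain neither exclusion.

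A second defence is that 3.5.1 introduces its benefit examples loosely, so a progressor might be judged not to have benefited. Section 5.3 closes that route by stating that benefit is determined by the Ki67 result or by membership of the 26.

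Two limits stand. The off-study rule already removes a confirmed new breast mass, so a reader who inferred that all confirmed breast progression is left open would go too far. The post-operative schema figure is not shown, and a condition drawn there cannot be ruled out.

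**Conclusion.** Wrong as written. The stated rules leave adjuvant PD 0332991 open after confirmed primary or nodal growth on that drug and closed after unconfirmed growth, and 5.7 disagrees with 3.5 and Appendix C about the second group. This rests on the available text and on the ordinary reading of the 5.7 paragraph.

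The size is unknown: the documents do not allow the number of women affected to be derived. The ceiling of 63 counts adjuvant candidates, not progressors, and 26 of them are a fixed group already enrolled.

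Four stronger readings are tempting but not supported:

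- **That tumour measurements play no part in adjuvant eligibility.** This holds for 3.5 and 5.3, but under 5.7 those measurements trigger the imaging on which the bar depends.
- **That the 97 of 112 days measure the defect.** They show only that progression can follow the Ki67 test.
- **That the adjuvant safety objective is distorted.** Adverse events are summarised descriptively, and nothing in the documents shows how earlier local growth would bias that summary.
- **That the sentence was certainly misplaced.** This is plausible, but it remains an inference.

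The C1D15 primary endpoint and the sample sizes are untouched. The change is worth making because it is cheap and concerns who is exposed to drug.

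**What to change.** - Add to 3.5.2 and Appendix C the exclusion *imaging-confirmed progression of the primary tumor or axillary nodes during neoadjuvant PD 0332991 treatment*. The limit to PD 0332991 is needed because 3.4 admits women after other neoadjuvant endocrine therapy and does not exclude progression on it. A wider wording could bar a woman who progressed before the study drug and then responded to it.
- In 5.7, move the bar to the confirmed-progression paragraph. If a bar on unconfirmed progression is intended, keep it and repeat it in 3.5.2 and Appendix C.
- In 10.3, change the reference from Section 3.4 to Section 3.5, and the Ki67 condition from <10% to ≤10%.

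The cost is a short amendment and a revised worksheet. Any woman with confirmed progression on the drug who would now qualify loses access to it. No new data are needed, since progression is already assessed during neoadjuvant treatment. Endpoints and sample sizes do not change.

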⁶Anastrozole is continued until the day of surgery. If premenopausal continue goserelin 3.6 mg SC monthly throughout the neoadjuvant duration. PD0332991 is also continued until the day of surgery in patients who started cycle 5 therapy.

⁷ See Postoperative Therapy and Follow-up Schema

*NCI9170: A phase II trial of neoadjuvant MK-2206 in combination with anastrozole for PIK3CA mutant clinical stage 2 or 3 ER+ and HER2- breast cancer

[†]If the NCI9170 trial is not open or was open but is now closed at the participating institution

POSTOPERATIVE THERAPY AND FOLLOW-UP SCHEMA

Except those who refuse for followup or did not undergo surgery

* Follow-up for patients who do not receive adjuvant PD 0332991 will take place annually for 5 years post-surgery or until recurrence (whichever comes first). Follow-up for patients who do receive adjuvant PD 0332991 will be tied to treatment, not to date of surgery. These patients will be followed for a total of 5 years (inclusive of the up to 2 years of adjuvant PD 0332991 treatment), with follow-up after discontinuation of PD 0332991 taking place annually after the last dose or until recurrence (whichever comes first). Patients who discontinue adjuvant PD 0332991 early (do not complete the full 23 cycles of treatment) will be followed annually following the last dose of PD 0332991 to get as close as possible to 5 years of post-surgery follow-up or until recurrence (whichever comes first).

¹ Endocrine therapy that is not Anastrozole can be used if patient cannot tolerate Anastrozole (See Section 5.3)

Glossary of Abbreviations

AE	Adverse event
ALT (SGPT)	Alanine transaminase (serum glutamate pyruvic transaminase)
ANC	Absolute neutrophil count
AST (SGOT)	Aspartate transaminase (serum glutamic oxaloacetic transaminase)
AUC	Area under the curve
BCS	Breast conserving surgery
B-HCG	Beta human chorionic gonadotropin
BUN	Blood urea nitrogen
CBC	Complete blood count
Cdk	Cyclin dependent kinase
CFR	Code of Federal Regulations
CNS	Central nervous system
CR	Complete response
CRF	Case report form
CT	Computed tomography
CTCAE	Common Terminology Criteria for Adverse Events
CTEP	Cancer Therapy Evaluation Program
DCIS	Ductal carcinoma in situ
DNA	deoxyribonucleic acid
DOB	Date of birth
DSM	Data and Safety Monitoring
DSMC	Data Safety Monitoring Committee
ECG (or EKG)	Electrocardiogram
ECOG	Eastern Cooperative Oncology Group
EDTA	ethylenediaminetetraacetic acid
ER	Estrogen receptor
FDA	Food and Drug Administration

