in the PIK3CA WT cohort and all 15 (100%, 90% CI: 82-100%) patients in the PIK3CA mutant cohort. The study met its primary endpoint of achieving a CCCA rate of 66% in C1D15. In addition, 26 patients who did not achieve CCCA with anastrozole alone on C1D1 achieved complete CCCA in C1D15 post 2 weeks of combination therapy. These data justify the evaluation of PD 0332991 in the adjuvant setting. The international PALLAS (PALbociclib CoLlaborative Adjuvant Study) trial is currently enrolling patients with high risk ER+ HER2- breast cancer to receive 2 years of palbociclib (PD 0332991) in the adjuvant setting. However, patients who received neoadjuvant PD 0332991 (palbociclib) are not eligible for the adjuvant PALLAS trial. We therefore propose to include in this trial the option of adjuvant PD 0332991 with anastrozole for 23 cycles after chemotherapy and radiation therapy for those who derived benefit from PD 0332991 in the neoadjuvant setting in this trial. This includes:

- The 26 patients who achieved complete cell cycle arrest only after the addition of PD 0332991 (C1D1 Ki67 $>2.7\%$ and C1D15 Ki67 $\leq 2.7\%$) (in the PIK3CA WT, mutant, or unknown cohorts).
- Patients who have a Ki67 $\leq 10\%$ on C1D15 biopsy in the endocrine resistant cohort (including patients enrolled prior to activation of Amendment #7).

All patients (with the exception of those who withdraw consent for follow-up and those who did not undergo surgery) will be followed for invasive disease recurrence and overall survival for 5 years in the adjuvant setting or until recurrence (whichever comes first). Blood will be drawn for serum, plasma, and circulating cell-free DNA (cfDNA) yearly.

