5.6 Duration of Therapy

If at any time the constraints of this protocol are considered to be detrimental to the patient's health and/or the patient no longer wishes to continue protocol therapy, the protocol therapy should be discontinued and the reason(s) for discontinuation documented in the case report forms.

In the absence of treatment delays due to adverse events, neoadjuvant treatment may continue for 4 cycles plus the fifth short cycle or one of the following criteria applies:

- Documented and confirmed disease progression or Ki67>10 % on C1D15
- Death
- Adverse event(s) that, in the judgment of the investigator, may cause severe or permanent harm or which rule out continuation of study drug
- General or specific changes in the patient's condition render the patient unacceptable for further treatment in the judgment of the investigator
- Suspected pregnancy
- Serious non-compliance with the study protocol
- Lost to follow-up
- Patient withdraws consent
- Investigator removes the patient from study
- The Siteman Cancer Center decides to close the study

Adjuvant treatment (in patients eligible to receive it) may continue for up to 23 cycles or until one of the following criteria applies:

- Documented and confirmed disease progression
- Death
- Adverse event(s) that, in the judgment of the investigator, may cause severe or permanent harm or which rule out continuation of study drug
- General or specific changes in the patient's condition render the patient unacceptable for further treatment in the judgment of the investigator
- Suspected pregnancy
- Serious non-compliance with the study protocol (missing 50% dosing in any cycle due to non-compliance or missing study required procedures due to non-compliance determined by site investigator)
- Lost to follow-up
- Patient withdraws consent
- Investigator removes the patient from study
- The Siteman Cancer Center decides to close the study

Patients who prematurely discontinue treatment for any reason will be followed as indicated in the study calendar.

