15.5 Data Analysis

All data analyses will be performed separately for each cohort unless otherwise specified.

Demographic and clinical characteristics of the sample, as well as response, toxicity by grade, and loss to follow-up will be summarized using descriptive statistics. The rate of complete cell cycle arrest will be calculated and the corresponding 90% confidence interval (CI) will be provided. The rates for pCR and PEPI 0 and their 90% CIs will also be calculated. The differences in overall survival (OS) and relapse-free survival (RFS) for patients with or without complete cell cycle arrest on C1D1 will be described using Kaplan-Meier product limit estimator and compared by log-rank tests. Similar analysis will be performed for complete cell cycle arrest on C1D15 or patients with or without PEPI 0, with the two cohorts combined or separately. A trajectory analysis (see below) will also be performed for this comparison.

Analysis of other secondary endpoints:

Clinical response rate: The clinical response rate will be estimated by the number of patients whose disease meets the WHO criteria of complete or partial response prior to surgery divided by the total number of eligible patients who began combination neoadjuvant treatment. A 90% confidence interval for the true clinical response rate will be calculated using the Duffy-Santner approach for the endocrine resistant cohort (2-stage design). The complete cell cycle arrest rates and the corresponding 90% confidence intervals will also be calculated for PIK3CA wild type and mutant cohorts separately and combined.

Radiological response rate: The radiological response rate will be estimated by the number of patients whose disease meets with WHO criteria for complete or partial response at the evaluation prior to surgery divided by the total number of eligible patients who began

combination neo-adjuvant therapy. A 90% confidence interval for the true radiographic response rate will be calculated using the Duffy-Santner approach. The analysis will be performed with the two cohorts separately and combined.

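### Treated women who never have surgery are not followed beyond 30-60 days, so OS and RFS by arrest status come from a set selected after the groups are formed

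*Combined protocol and SAP*

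**What the plan says.** **Follow-up without surgery.** Section 5.7 (Treatment/Follow-up Decision Tree): "Patients in whom surgery is not performed will be observed for 30-60 days after last dose of study drug"; such women "will not undergo annual follow-up". The Postoperative Therapy and Follow-up Schema has the same exception: "Except those who refuse for followup or did not undergo surgery". So does Section 1.8: "All patients (with the exception of those who withdraw consent for follow-up and those who did not undergo surgery) will be followed".

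**Progression away from the primary tumour.** When this is confirmed, Section 5.7 stops the study drug and ends: "Subsequent management is at the investigator's discretion. The patient will go off study". It gives no later survival follow-up for these women.

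**Who is followed.** Three statements differ. One paragraph of 5.7 leaves out women who refused surgery (or withdrew consent for follow-up). A later one leaves out anyone not operated on, for whatever reason. Section 5.8 covers everyone who receives study therapy, but times her follow-up from surgery.

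**Early stopping.** Section 5.6: "Patients who prematurely discontinue treatment for any reason will be followed as indicated in the study calendar". In the 10.2 calendar, footnote C counts the yearly contacts from surgery. The Follow-Up Form in Section 11 is also scheduled from surgery.

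**Analysis.** Secondary Objective 10 concerns the long-term outcomes of patients treated in the trial. Section 15.5 plans Kaplan-Meier and log-rank comparisons: "The differences in overall survival (OS) and relapse-free survival (RFS) for patients with or without complete cell cycle arrest" on C1D1, with a similar analysis for C1D15. It gives no time origin, no censoring rule and no handling of women without surgery.

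**The concern.** Arrest status is known at C1D1 and C1D15. Surgery comes months later, and whether a woman has it may depend on how her disease behaves in between. Following only operated women therefore filters the comparison groups after they are formed. A woman found to have advanced disease during neoadjuvant treatment, or who cannot be operated on, plausibly has a poor prognosis, and her later death is not collected.

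At stake are the trial-level OS and RFS estimates, which would describe operated rather than treated women, and the comparison by arrest status, where one group is very small. Analysis cannot repair the loss if the outcomes were never recorded.

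**Working it through.** **1. Is there any route to long-term follow-up without surgery?**

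| Place | Rule | Unoperated woman |
|---|---|---|
| Follow-up schema, 1.8, 5.7 | Explicit exception | Not followed yearly |
| 5.7, Ki67 >10% or primary-site progression | Yearly to 5 years after surgery | No start date |
| 5.8 | All who receive study therapy, timed from surgery | No start date |
| 5.6 | Refers to the calendar | Back to 10.2 |
| 10.2 footnote C | 30-60 days after surgery, then yearly | No start date |
| 10.2 progression column | One off-study assessment | Seen once, not yearly |
| Section 11, Follow-Up Form | Yearly for 5 years after surgery | No form due |

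No route exists. What is lost is everything after the 30-60 day window.

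**2. Size of the smaller group.** Section 1.8 reports C1D15 arrest in 39 of 45 evaluable women in the PIK3CA cohorts. 45 − 39 = 6 without arrest; 1/6 = 17% per woman lost.

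**3. Direction of the bias.** The plan states no figure for this comparison, so there is none to reproduce. The inputs are assumptions:

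- 5-year RFS of 85% with arrest and 60% without. These are the best and worst Ki67 groups of the IMPACT trial as quoted in Section 1.9.1, used only as a scale.
- 90% 5-year event risk in an unoperated woman.
- Unoperated women are removed from the analysis.

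With n women in a group, event share e and m removed, the observed event share is (n·e − 0.9m)/(n − m). The hazard ratio, no arrest versus arrest, is ln(1 − share without arrest)/ln(1 − share with arrest). With no loss it is ln 0.60/ln 0.85 = 3.1.

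| Lost, no arrest (of 6) | Lost, arrest (of 39) | Event share, no arrest | Event share, arrest | Hazard ratio |
|---|---|---|---|---|
| 0 | 0 | 0.40 | 0.15 | 3.1 |
| 1 | 0 | (2.4 − 0.9)/5 = 0.30 | 0.15 | 2.2 |
| 2 | 0 | (2.4 − 1.8)/4 = 0.15 | 0.15 | 1.0 |
| 1 | 2 | 0.30 | (5.85 − 1.8)/37 = 0.109 | 3.1 |
| 1 | 3 | 0.30 | (5.85 − 2.7)/36 = 0.0875 | 3.9 |

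A large-sample simulation that instead censors unoperated women at 60 days agrees. Loss of 17% without arrest and none with arrest takes the hazard ratio from about 3.3 to 2.3. Equal loss of 10% in both groups takes it from about 3.1 to 5.4.

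**4. How much the comparison can show in any case.** Expected events are 39 × 0.15 + 6 × 0.40 = 8.25. By Schoenfeld's formula at two-sided 5%, z = √(8.25 × (6/45) × (39/45)) × ln 3.14 − 1.96 = −0.84, so power is about 20% even with complete follow-up.

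**The case against.** **Many high-risk women are followed.** Those stopped for C1D15 Ki67 above 10%, and those with confirmed primary-site progression, have yearly follow-up once they are operated on. A woman who progresses elsewhere may also go to surgery, since 5.7 allows her samples to be taken then, and 1.8 and 5.8 would then cover her. For her the off-study sentence is an inconsistency to reconcile and does not prove loss. This stands, and it confines the point to women never operated on.

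**Progression before surgery is recorded.** Section 12.1 counts new lesions as progressive disease, and 12.2 counts progression during neoadjuvant therapy as resistance. A reader might infer that a progressing woman has no visit, or that 5.6 promises what 5.7 denies. Neither holds: the 10.2 calendar has an off-study progression assessment, and 5.6 only points to that calendar. Yearly contact is what is missing. For RFS the main gap is that 15.5 does not say whether a recorded progression counts or when time starts; 12.4 defines recurrence only after surgery.

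**A post-surgical RFS is a coherent choice.** True, and it can be kept as a display. It does not serve OS, or a comparison of groups fixed before surgery.

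**The comparison is secondary and weak.** Also true; the primary Ki67 endpoint is untouched. Low power limits what is at stake but does not justify leaving deaths uncollected when collection is cheap.

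**Conclusion.** The gap is real: as written, the plan collects no deaths or disease events beyond 30-60 days after the last dose in treated women who are not operated on, although its objective and analyses concern all women treated. The statements in 5.7 and 5.8 on who is followed also differ and must be reconciled.

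A reader might infer that the loss necessarily flatters the group without arrest and shrinks the contrast. The documents do not support that. They give no count of unoperated women, overall or by arrest status, and the count could be zero. Under the assumptions above, the hazard ratio falls if loss is confined to women without arrest. It is unchanged at 1 of 6 and 2 of 39 lost, and rises at 1 of 6 and 3 of 39, where the loss rate without arrest is still about twice as high (17% against 8%). Size and direction are unknown; the firm figure is 17% of the non-arrest group per woman lost.

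This is a worthwhile, inexpensive correction to a secondary analysis. It also matters for the endocrine resistant cohort, which remained open at Amendment #7.

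**What to change.** **Follow-up.** In the schema note, 1.8, 5.7, 5.8, 10.2 footnote C and the Follow-Up Form schedule in Section 11, replace the no-surgery exception. Every woman who took PD 0332991 and has not withdrawn consent for follow-up has yearly vital and disease status, by phone or chart, to 5 years. In 5.7, change the off-study sentence to off study treatment, so that follow-up continues. Collect vital status on the same basis in operated and unoperated women. The current rules stop follow-up at recurrence, and leaving that stop for operated women only would make death ascertainment uneven.

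**Analysis (15.5).**
- Start OS by C1D15 arrest at C1D15, and OS by C1D1 arrest at C1D1, in all treated women with that Ki67 value.
- State how distant progression recorded before surgery counts in the RFS comparison by arrest status. Whether inoperability itself should be an event is debatable and is not proposed here.
- Report the number of unoperated women by arrest status.
- Keep the surgery-based RFS curve as a secondary display.

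**Cost.** Protocol wording and a few yearly contacts, with no new clinic visit, sample or procedure. Women from the closed PIK3CA cohorts who have already left follow-up may need re-contact, and RFS would no longer be counted only from surgery.
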